### 3. STUDY DESIGN

Study design: prospective randomized controlled trial.

Patients will be randomized to biomarker-guided treatment (based on blood procalcitonin level) or to usual care. In the usual care arm, and in the biomarker guided-arm in case of high procalcitonin, patients will receive amoxicillin-clavulanic acid.

Prednisolone will be given during 5 days and with a dose of 40mg/day in a single dose as recommended by the Dutch National Guideline (16).

Usual care	Physician's choice	Prednisolone ± antibiotics
PCT level guided care	PCT ≤ 0.25ug/L	Prednisolone
	PCT > 0.25ug/L	Prednisolone + amoxicillin-clavulanic acid

The procalcitonin will be measured in both groups but will only be reported for the patients randomised to the PCT group and not for patients in the usual care group during the study period. The measurement will be performed in the usual care group but this will be blinded until the study is completed.

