### **Statistical and analytical plans**

#### **Primary analysis**

The primary endpoint is defined as 30-day treatment failure. The per protocol (PP) population is the main analysis population. An analysis will be performed for the randomly

---

allocated antibiotic strategy (i.e. usual care versus antibiotics in patients with PCT >0.25 µg/L). The difference and corresponding 95% confidence interval (two-sided) in the incidence of the primary endpoint between the randomly allocated strategies (biomarker-guided drug use minus drug-in-all) will be determined. Non-inferiority will be concluded if the upper limit of the 95% confidence interval does not exceed the prespecified non-inferiority margin of 5%.

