5.2 Endpoints

The primary objective of this study is to show that at hospitalization for a severe exacerbation of COPD, PCT-guided treatment regarding antibiotic use is non-inferior to usual care consisting of prednisolone and or antibiotics, in terms of treatment failure at day 30 for patients hospitalized because of an acute exacerbation of COPD (AECOPD). Treatment failure is defined as disease-related mortality, endotracheal intubation, vasopressors, renal failure, lung abscess/empyema, pneumonia development or hospital readmission within 30 days after inclusion of the study.

The secondary objectives of this study are to assess the following secondary endpoints:

- Treatment failure defined as an incomplete resolution of the clinical signs and symptoms associated with the AECOPD at day 30 after inclusion of the study (i.e not reaching the baseline condition prior to the AECOPD) scored using the modified Anthonisen criteria.
- Change in Quality of Life on day 1, 10, and after 30 days using the COPD Assessment Test (CAT)
- EXACT – Respiratory symptoms scale (at admission, at day 10 and at day 30 after admission)
- Time to complete resolution of symptoms according to daily symptom diaries evaluating the modified Anthonisen criteria
- Start of antibiotic therapy after an initial opposite decision (after 48 hours)
- Non-Invasive ventilation after 72 hours of admission
- Length of hospitalization
- Re-exacerbation within 30 days
- Side effects (gastro-intestinal complaints, allergic reactions)
- Cumulative antibiotic consumption
- Cumulative prednisolone consumption

6 Study Methods

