8.2.2 Per Protocol Population

- All subjects who:
 - met all inclusion/exclusion criteria,
 - attained a sufficient compliance to the treatment received, treatment with prednisolone and/or antibiotics, when prescribed on admission for at least 5 days,
 - did not present serious deviations from the protocol.

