9.2 Derived variables

The primary endpoint consists of several variables: disease-related mortality, endotracheal intubation, vasopressors, renal failure, lung abscess/empyema, pneumonia development and hospital readmission.

The key secondary endpoint is derived from the scores of the diary card with the modified Anthonisen criteria* the patient will fill in on baseline, day 3, day 5, day 10 and day 30. This endpoint will be scored by an independent physician. If there is incomplete resolution of symptoms, this will result in treatment failure. The symptoms are scored as categorical variables and include shortness of breath (slightly or much worse or 'as baseline condition prior to exacerbation'), sputum production (slightly or much more or 'as baseline condition prior to exacerbation'), sputum discoloration (slightly or strongly increased or 'as baseline condition prior to exacerbation') and minor symptoms as coughing, sore throat, fever, wheezing or a blocked or running nose. When one of these symptoms has not been resolved on day 30 this should result in scoring this as treatment failure.

*Example of the diary card with the modified Anthonisen criteria we used to derive our own diary card in Dutch. This original diary card was designed by Jaap Trappenburg et al. and used in a trial that was published in 2011 [15](Thorax 2011;66:977e984):

After evening diner

Compared with previous weeks ...	DAY 1 _/_/2009	DAY 1 _/_/2009	DAY 1 _/_/2009
I am more short of breath than normal	 No  Yes, slightly increased  Yes, clearly increased	 No  Yes, slightly increased  Yes, clearly increased	 No  Yes, slightly increased  Yes, clearly increased
I produce more sputum than normal	 No  Yes, slightly increased  Yes, clearly increased	 No  Yes, slightly increased  Yes, clearly increased	 No  Yes, slightly increased  Yes, clearly increased

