9.3 Protocol Deviations

When a physician decides to prescribe antibiotic therapy even though the patient has a low serum concentration of procalcitonin ($\leq 0.25 \mu\text{g/mL}$) this leads to a protocol violation. The patient might recover because of the antibiotic therapy instead of still experiencing symptoms on day 30, which could directly impact the primary endpoint. This subject should not be analyzed in the per protocol analysis, because of this major protocol deviation/violation.

Early termination of antibiotic therapy, in both groups, could have an impact on the primary endpoint. This could happen when a patient has an initial quick recovery and gets discharged from the hospital without antibiotic therapy and then has a relapse. We do not expect this to happen more in one of the two treatment arms, although a high PCT might lead to less frequent discontinuation of the treatment when the patient is discharged in the first 5 days (the antibiotic therapy should be given during 5 days in both groups).

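### SAP 9.3 removes low-PCT patients given antibiotics from the deciding per-protocol set without naming an arm or a time limit, so one arm can be selected after randomisation and late starts can drop out of Table 2

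*SAP*

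**What the plan says.** **Deciding set.** Protocol 10 (Primary analysis) states: "The per protocol (PP) population is the main analysis population". SAP 8.2.3, 10 and 10.2.1 agree and make intention-to-treat (ITT) secondary. Both sets are planned for all efficacy variables as a robustness check. Neither document says what happens to the claim if they disagree.

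**The exclusion.** SAP 9.3 treats an antibiotic prescription despite PCT at or below the cut-off as a violation: "This subject should not be analyzed in the per protocol analysis, because of this major protocol deviation/violation". Its reason is: "The patient might recover because of the antibiotic therapy instead of still experiencing symptoms on day 30". The paragraph names no arm and no time window. The next one, on early termination, does refer to both groups.

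**Usual care.** Under Protocol 3, PCT "will only be reported for the patients randomised to the PCT group and not for patients in the usual care group". Protocol 5 leaves antibiotics in that arm to clinical judgement.

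**Endpoints.** The primary composite in SAP 5.2 is disease-related death, intubation, vasopressors, "renal failure, lung abscess/empyema, pneumonia development or hospital readmission within 30 days after inclusion of the study". Symptoms at day 30 belong elsewhere. SAP 9.2 says: "The key secondary endpoint is derived from the scores of the diary card with the modified Anthonisen criteria".

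**Late starts.** SAP 5.2 lists a secondary endpoint: "Start of antibiotic therapy after an initial opposite decision (after 48 hours"). It has a row in Table 2, as has cumulative antibiotic consumption in days. SAP 9 and 17 base Table 2 on PP.

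**PP compliance.** SAP 8.2.2 ties compliance to "treatment with prednisolone and/or antibiotics, when prescribed on admission for at least 5 days". A separate criterion excludes serious deviations.

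**The concern.** An exclusion triggered by a treatment decision after randomisation is unlikely to be random: physicians override a low PCT in patients who worry them. If this happens in one arm only, the set that carries the confirmatory claim is no longer balanced by randomisation, and the error rate of the test can drift.

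With no time limit, a low-PCT patient who develops pneumonia and is then treated leaves the primary analysis together with the event. The same wording removes the patients whom the late-start endpoint is meant to count. Two analysts following SAP 9.3 could build different primary sets.

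**Working it through.** **1. The plan's own sample size.** Inputs (Protocol 4.4 and 10.4): 20.4% usual care, 16.7% PCT arm, margin 5 points, power 80%.

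n = (z₁₋α + z₁₋β)² × [0.204×0.796 + 0.167×0.833] / (0.05 + 0.037)²

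- One-sided 0.025: 312.6, so 313 per arm, as stated.
- One-sided 0.0246 (half of 0.0492): 314.2, so 315, as stated.

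Below I use 346 × 0.9 = 311.4 per arm (693 enrolled, 10% drop-out).

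**2. Which arm.** A physician can knowingly override a low PCT only where PCT is reported, which is the PCT arm. In usual care, prescribing is the strategy itself. If the rule were instead applied to usual care after unblinding, with 65% treated (Protocol 1) independently of PCT and 60% to 90% low PCT (both assumptions), 39% to 59% of that arm would go, leaving 131 to 192 of 315. The arm must therefore be named.

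**3. Which time.** SAP 9.3 works through the serious-deviation criterion, which has no window. The words on treatment at admission sit in the separate compliance criterion. They support a narrower reading (override of the initial decision) but do not impose it.

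**4. Effect on the primary test.** Truth at the margin: 25.4% against 20.4%. Let o be the share of the PCT arm removed and f the failure rate among those removed; the documents give neither. No one is removed from usual care.

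PP rate = (0.254 − o·f)/(1 − o); d = PP rate − 0.204; error = Φ((0.05 − d)/SE − 1.96), with unpooled SE.

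Example, o = 0.10 and f = 0.40: rate (0.254 − 0.040)/0.90 = 0.2378, d = 0.0338, SE = 0.0342, error 6.9%.

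| f (o = 10%) | d, points | one-sided type I error |
|---|---|---|
| 15% | 6.2 | 1.1% |
| 20% | 5.6 | 1.6% |
| 25.4% (uninformative) | 5.0 | 2.5% |
| 30% | 4.5 | 3.5% |
| 40% | 3.4 | 6.9% |

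For f from 15% to 40%, the range is 1.7% to 4.2% with 5% removed and 0.7% to 11.3% with 15% removed.

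**5. If usual care also loses patients.** Keep o = 0.10 and f = 0.40, and remove usual-care patients with the same 40% failure rate. With 5% removed, the usual-care rate is (0.204 − 0.020)/0.95 = 0.1937 and the error is 3.7%. With 10% removed, the rate is 0.1822 and the error is 1.7%.

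**6. As-written reading only: failures themselves removed.** If a share q of PCT-arm failures leaves PP, the rate is (0.254 − 0.254q)/(1 − 0.254q). For q = 5% (about 4 patients) it is 24.4% and the error is 4.7%. For q = 10% (about 8 patients) it is 23.5% and the error is 8.4%.

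**7. Table 2.** As written, a late start in a low-PCT patient of the PCT arm is also the reason for exclusion, so that patient cannot appear in the late-start row.

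For antibiotic days, let L be the low-PCT share, r the share of those overridden and k the days per override (all assumed), with 5 days for high PCT. PP mean = 5(1 − L)/(1 − L·r); all-randomised mean = 5(1 − L) + L·r·k. At L = 70% and r = 20%, PP gives 1.74 days; all randomised gives 1.64, 1.78 or 2.20 for k = 1, 2 or 5. PP is the lower figure only if k exceeds the PP mean.

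**The case against.** The strongest reply is that SAP 9.3 describes disregarding a known test result. PCT is measured once, at baseline. Later starts are a planned endpoint, so the trial expects them. It is inconsistent to read the sentence by its purpose for the arm and literally for time. This has force: the narrower reading may well be the intended one. But the text does not state it, and even that reading leaves selection by clinical judgement in one arm.

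PP as the primary set is a deliberate choice, which SAP 8.5.4 justifies by the non-inferiority design. That stands. The issue is the unbounded exclusion, not PP itself. The compliance criterion applies to both arms, so usual care can lose patients too, and step 5 shows that this can cancel the effect.

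The error figures use the risk-difference interval of Protocol 10, whereas SAP 10.1 decides on an odds-ratio interval. The SAP states the margin only as 5%, so no odds-ratio version was computed.

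Three stronger inferences are tempting and unsupported:

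- That the rule favours the PCT strategy. The direction depends on the prognosis of those removed, which the documents do not give.
- That Table 2 would understate the share of the PCT arm treated. It has no such row, and for days the sign is open.
- That late starts would go unreported. An ITT analysis of all efficacy variables is planned; it is just not what Table 2 shows.

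**Conclusion.** The concern holds as a should-fix. SAP 9.3 lets a post-randomisation treatment decision, in practice confined to the PCT arm, determine who enters the deciding set, and leaves open whether later treatment counts. Its rationale fits the key secondary endpoint, not the current primary composite. Under the as-written reading, the late-start row in Table 2 is about zero for low-PCT patients in the PCT arm by construction, and antibiotic days are distorted with unknown sign.

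The size for the primary test is illustrative. The range of 1.1% to 6.9% assumes 10% of the PCT arm removed, none of usual care, and 15% to 40% of those removed failing. The range of 4.7% to 8.4% applies only if 5% to 10% of PCT-arm failures are themselves removed. Neither range is a bound or a forecast. The textual defect does not depend on them.

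**What to change.** - **SAP 9.3, scope.** State that the exclusion applies to the PCT arm and only to an override of the initial PCT-based decision, for example before the 48-hour point already used for late starts. Antibiotics started later, after deterioration or an endpoint event, then do not remove a patient from PP.
- **SAP 9.3, rationale.** Rewrite it for the current primary endpoint.
- **Table 2.** Analyse and show late antibiotic start and cumulative antibiotic consumption on all randomised patients by allocated strategy, with PP as supportive.
- **Primary endpoint.** Report the all-randomised result beside PP and state that a non-inferiority claim needs the two to be consistent.
- **Minor.** Define ITT as all randomised patients, without the undefined study-drug condition. Reconcile the PCT unit in SAP 9.3 (µg/mL) with Protocol 3 and 10 and SAP 6.1 (µg/L).

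The cost is SAP wording and a short protocol clarification, since both analyses are already planned. The consistency requirement is the more debatable part because it costs power. At the design rates, with 311 per arm and 10% of the PCT arm removed (15% to 40% of them failing), simulated power under a strict both-sets rule is about 75% to 80%. PP alone gives 76% to 95% and ITT alone 80%. In return, type I error at the margin stays at 1.1% to 2.5% in the same removal scenarios.

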9.4 Demographic and Baseline Variables

The summary statistics will be produced in accordance with section 9.

9.5 Concurrent Illnesses and Medical Conditions

The summary statistics will be produced in accordance with section 9.

10 Efficacy Analyses

- Summary statistics that will be produced for continuous and categorical data:
 - The quality of life endpoints, using the COPD Assessment Test (CAT) and the EXACT-respiratory symptoms questionnaire, consist of multiple (three) measurements per subject. These measurements are all performed on the same time point (baseline, day 10 and day 30). These endpoints will be scored using the mean score and standard deviation when normally distributed and a median with the inter quartile range when the data have a skewed distribution. These data will be analyzed with a mixed effects model with random effects for center and patient to account for the extra hierarchical level in the data. The residuals will be evaluated for normality to test the assumptions of the models. In case of violations, transformations will be conducted on the dependent variable.
 - The unpaired continuous variables will be scored using the mean score and the standard deviation (normal distribution) or the median with the inter quartile range (skewed distribution). These variables will be analyzed using an mixed effects model.
 - The frequency and percentage will be reported for the categorical (mostly dichotomous) variables. Analysis of these variables will be performed using a logistic mixed-effects model.

- Analysis populations that will be used and identification of the primary population.
 - We will analyze the population with a per-protocol analysis and an intention-to-treat analysis. The primary population will be the per-protocol population.

- A statement of the clinical objective rephrased in precise statistical terms (null and alternative hypotheses):
 - Null hypothesis: PCT-guided treatment regarding antibiotic use is inferior to usual care in patients with an acute exacerbation of COPD
 - Alternative hypothesis: PCT-guided treatment regarding antibiotic use is non-inferior to usual care in patients with an acute exacerbation of COPD
- The nature of the hypothesis is confirmatory

10.1 Primary Efficacy Analysis

The summary statistics will be produced in accordance with section 9.

The non-inferiority of the treatment will be decided based on the 95% confidence interval of the OR from the logistic mixed model for the treatment arm versus the usual care arm.

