Plan for statistical analysis	
Primary analysis The primary endpoint is defined as 30-day treatment failure. The per protocol (PP) population is the main analysis population. The difference and corresponding 95% confidence interval (two-sided) in the incidence of the primary endpoint between the randomly allocated strategies (biomarker-guided antibiotic use minus usual care) will be determined. Non-inferiority will be concluded if the upper limit of this confidence interval does not exceed the prespecified non-inferiority margin of 5%.
 
Secondary analyses Differences in the incidence of these secondary endpoints between randomly allocated strategies will be analyzed by chi-square tests and logistic regression.

---

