In international literature there is scarce information about the percentages of treatment failure in patients admitted with an AECOPD receiving usual care. Therefore, we have performed a further search on PCT studies with a primary outcome of 30-day treatment failure. In the study by Schuetz et al. [6], who studied patients with lower respiratory tract infection, 30-day treatment failure was observed in 15.5% of the patients randomised to biomarker-based treatment, as compared to 18.9% in those randomised to usual care. This implies a relative risk of 0.82 in favour of the biomarker-based strategy. The study by Schuetz et al. was designed as a non-inferiority study, using a non-inferiority boundary of 7.5%. In view of these data we decided to design our study as a non-inferior study, whereas we choose a non-inferiority boundary of 5.0%. We based the primary outcome on the study of Huang et al. [13]. The incidence of the primary outcome was 20.4%. Using the relative risk of 0.82 in favour of the PCT-guided treatment group we expect the incidence of the primary outcome to be 16.7% in the PCT-guided treatment group. Then a total sample size of 626 is required (313 per treatment arm) to demonstrate non-inferiority with a power of 80%, and applying a one-sided alpha error of 0.025. We aim to enroll a total of 690 patients, accounting for a 10% drop-out rate.

8 General Analysis Considerations

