8.6 Multiple Testing

Op dit moment niet van toepassing, mogelijk nog wanneer primair eindpunt zou veranderen.

9 Summary of Study Data

Table 1. Baseline characteristics

The baseline characteristics are given in the table below.

	Usual care (n = 308)	PCT-guided treatment (n = 308)
Age in years – mean±SD		
Male gender – no. (%)		
BMI – mean±SD		
Smoking status: - current – no. (%) - past – no. (%) - pack years (mean, range)		
FEV1 % predicted - mean±SD		
GOLD classification: - I – no. (%) - II – no. (%) - III – no. (%) - IV – no. (%)		
Exacerbation type: - type I – no. (%) - type II – no. (%) - type III – no. (%)		
Median duration of symptoms in days - mean±SD		
CRP in mg/L – median [IQR]		
WBC 10 ⁹ /L – mean±SD		
CAT score – median [IQR]		
EXACT- RS score – median [IQR]		

Primary outcome

The primary outcome will be treatment failure within 30 days. A non-inferiority margin of 5% will be used to assess non-inferiority. Treatment failure is defined as disease-related mortality, endotracheal intubation, vasopressors, renal failure, lung abscess/empyema, development of pneumonia and hospital readmission within 30 days.

- Binary outcome parameter: yes or no. Description: number and percentage.
- To account for the multicenter effect a logistic mixed effects model will be estimated with

centers as random effect and treatment group as fixed effect to analyze the primary outcome. The risk of primary endpoint in the PCT guided treatment arm versus the usual care treatment arm will be reported with an odds ratio from the logistic model, with a 95% confidence interval. Based on this CI we will determine non-inferiority of the treatment.

Secondary outcome parameters

Skewed data will be analyzed using non-parametric tests. Paired measurements will be analyzed using paired tests.

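### The SAP decides non-inferiority on an odds-ratio confidence interval, but the only margin is 5 percentage points on the risk-difference scale

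*SAP*

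**What the plan says.** **Protocol.** The synopsis and the primary analysis paragraph after section 10.3 use the same effect measure: "The difference and corresponding 95% confidence interval (two-sided) in the incidence of the primary endpoint between the randomly allocated strategies", taken as biomarker-guided minus the comparator. The decision rule in that paragraph is: "Non-inferiority will be concluded if the upper limit of the 95% confidence interval does not exceed the prespecified non-inferiority margin of 5"%.

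**SAP section 9, primary outcome.** The margin appears without a scale: "A non-inferiority margin of 5% will be used to assess non-inferiority". The model is a logistic mixed model with centre as random effect and treatment as fixed effect. Its output is an odds ratio: "The risk of primary endpoint in the PCT guided treatment arm versus the usual care treatment arm will be reported with an odds ratio". The SAP then says: "Based on this CI we will determine non-inferiority of the treatment".

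**SAP section 10.1.** The decision is restated: "The non-inferiority of the treatment will be decided based on the 95% confidence interval of the OR from the logistic mixed model", treatment arm versus usual care.

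**Elsewhere in the SAP.** The sample size section says "we choose a non-inferiority boundary of 5.0"%. The hypotheses in section 10 say only that PCT guidance is inferior or non-inferior; they name no parameter and no margin. Table 2 has an odds ratio with 95% CI for the primary endpoint and no risk difference. The list of tables in section 17 mentions OR, RR and RD for Table 2, but only to set the number of decimals.

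**The concern.** The two documents give different decision statistics for the same test, and the SAP's version lacks a limit. A margin of 5% has no defined meaning on an odds ratio. Turning 5 points into an odds ratio requires a control rate, and neither document says whether that should be the planned rate or the observed one. The odds ratio from a random-centre model is also conditional on centre, whereas the sample size was computed for a simple difference in proportions.

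This is the primary analysis, which SAP section 10 calls confirmatory. An analyst who follows the SAP has to supply an odds-ratio limit that is not prespecified, possibly with the data in hand, and the choice can change the verdict. The stated 80% power applies only to the risk-difference rule. Both documents also admit that information on failure rates under usual care is scarce, so a limit that depends on the control rate is on weak ground in this trial.

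**Working it through.** **Inputs**
- Usual-care failure rate p_C = 0.204 ("The incidence of the primary outcome was 20.4"%) and PCT-arm rate p_T = 0.167, both from the sample size sections.
- Margin 0.05, one-sided alpha 0.025, power 80%, 313 per arm (same sections).
- Final p-value 0.0492 and 315 per arm (protocol 10.4, SAP 8.5.5).
- Centre variance is not given. All odds-ratio figures below are Wald calculations without a centre effect.

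**Step 1. Reproduce the plan's sample size on the risk-difference scale**

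n per arm = (z_α + z_β)² × [p_C(1−p_C) + p_T(1−p_T)] / (margin + p_C − p_T)²

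- Variance sum: 0.204×0.796 + 0.167×0.833 = 0.1624 + 0.1391 = 0.3015.
- Distance to the margin: 0.05 + 0.204 − 0.167 = 0.087.
- At alpha 0.025: (1.960 + 0.842)² × 0.3015 / 0.087² = 312.6, so **313**, as stated.
- At alpha 0.0492/2 = 0.0246: 314.2, so **315**, as stated.

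The plan's numbers therefore treat 5% as an absolute difference.

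**Step 2. Odds ratio equivalent to +5 points**

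OR = [(p+0.05)/(1−p−0.05)] / [p/(1−p)]

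| Usual-care rate p | OR equal to +5 points | Points allowed by a fixed OR of 1.329 |
|---|---|---|
| 10% | 1.588 | 2.9 |
| 15% | 1.417 | 4.0 |
| 20.4% | 1.329 | 5.0 |
| 25% | 1.286 | 5.7 |
| 30% | 1.256 | 6.3 |

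**Step 3. Power at 315 per arm under the planning rates**
- Risk difference: SE = √(0.3015/315) = 0.0309. Then 0.087/0.0309 − 1.96 = 0.85, giving **80%**.
- Odds ratio: expected OR = (0.167/0.833)/(0.204/0.796) = 0.782, log OR = −0.246. SE = √{[1/(0.167×0.833) + 1/(0.204×0.796)]/315} = 0.206.
  - Limit 1.329: (0.284 + 0.246)/0.206 − 1.96 = 0.61, giving **73%**. Reaching 80% would need about 374 per arm.
  - Limit 1.05, if 5% were read directly as an odds ratio: (0.049 + 0.246)/0.206 − 1.96 = −0.53, giving **30%**. This limit is worth only 0.8 points at a 20.4% control rate.

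**Step 4. Same data, both rules (315 per arm, 95% Wald limits)**

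| Failures, PCT vs usual care | Upper limit, difference | Against 5 points | Upper limit, OR | Against 1.329 |
|---|---|---|---|---|
| 53 vs 64 | 2.58 points | pass | 1.187 | pass |
| 58 vs 64 | 4.26 points | pass | 1.315 | pass |
| 59 vs 64 | 4.60 points | pass | 1.341 | fail |
| 60 vs 64 | 4.94 points | pass | 1.367 | fail |
| 61 vs 64 | 5.28 points | fail | 1.393 | fail |
| 32 vs 32 | 4.72 points | pass | 1.677 | fail |

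The last row has about 10% failures in each arm. It also fails 1.588, the odds-ratio equivalent of 5 points at a 10% control rate.

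**The case against.** The protocol contains a complete prespecified rule: statistic, direction, interval and margin. The SAP lists the protocol among its study documents and repeats the 5.0% boundary next to the 20.4% rate. An analyst could apply the protocol rule, or convert 5 points at 20.4%, without seeing any outcome data. On this view a post-hoc choice is not forced. This is partly right, but the SAP does not say that the protocol prevails, gives no conversion, and states its own odds-ratio rule twice.

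The odds-ratio power figures rest on limits that the documents do not contain. The 73% assumes a limit fixed at the planning rate. The 30% assumes a reading of 5% that the protocol and the sample size argue against. Both are conditional illustrations of what the missing limit leaves open; neither describes the protocol's design, whose power is sound.

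Near the planned control rate the conflict is narrow. With 64 usual-care failures, the two rules disagree only at 59 and 60 PCT failures, and close to the planned effect (53 vs 64) both pass. That stands. The disagreement is larger when the control rate departs from plan, as the 32 vs 32 case shows.

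The difference between a centre-conditional and a marginal odds ratio cannot be quantified without a centre variance, so it adds little to the size of the problem.

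**Conclusion.** The concern holds and must be fixed before the analysis. The SAP's primary decision rule uses a different scale from the protocol and the sample size, and it has no limit to compare with. The sample size itself is correct on the risk-difference scale.

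Under the planning rates with 315 per arm, power is 80% by the protocol's rule and about 73% against the odds ratio equivalent to 5 points at 20.4%. That equivalent runs from 1.59 to 1.26 as the control rate goes from 10% to 30%, and the two rules can give opposite verdicts on the same data. The odds-ratio results assume Wald intervals, no centre effect, and illustrative limits, because the SAP supplies none. The contradiction and the missing limit do not depend on those assumptions.

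**What to change.** Rewrite the rule in SAP section 9 (primary outcome), the hypotheses in section 10, section 10.1 and Table 2:

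- The estimand for the decision is the risk difference in 30-day treatment failure, PCT-guided minus usual care. Non-inferiority is declared only if the upper confidence limit is at most 5 percentage points.
- Name the method. One choice is marginal standardisation of the planned logistic mixed model, stating how the random centre effects are handled and how the interval is computed. The other is a Mantel-Haenszel difference stratified by the randomisation strata. For the latter, first settle the strata: protocol 8.2 stratifies by centre and antibiotic pre-treatment, the SAP by centre only.
- State the confidence level. Both documents set the final p-value at 0.0492, which corresponds to a 95.08% interval, yet write 95% in the decision rule.
- Keep the odds ratio as a supportive summary, and add the risk difference with its interval to Table 2.

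The cost is SAP wording and a few lines of code, with no extra patients or data. A prespecified and justified odds-ratio margin in both documents would also remove the conflict. It would require the power to be redone, and at a limit of 1.33 about 374 per arm instead of 315 before drop-out.
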